1.3.2.2 Safety assessments

- Adverse Events

Adverse events (AEs) will be monitored from the time that the subject gives informed consent and throughout the study. AEs will be elicited by direct, nonleading questioning or by spontaneous reports.

AEs will be recorded and graded according to the current version of the National Cancer Institute Common Terminology Criteria for AEs (version 5.0, Dated 14 February 2018).

- Vital signs

Vital signs will be collected at Screening (Visit 1), IIP administration visit (Visit 2 Day 1 before IIP administration and at 0.5, 1, 2, 4 hours post-injection and on Day 2), and End of Study (Visit 3)/Early Withdrawal.

Blood pressure (systolic and diastolic) and heart rate will be assessed with an automated device so that measurements are independent of the observer. These parameters will be recorded after five minutes rest in sitting position and after one minute standing.

Respiratory rate and temperature (tympanic/oral) will also be recorded.

Any clinically significant abnormalities will be recorded as AEs.

- **Physical Examination**

Physical examination and body weight will be conducted at Screening (Visit 1), IIP administration visit (Visit 2 Day 1, Pre-Dose), and End of Study (Visit 3)/Early Withdrawal. Height will be measured at Screening.

Any clinically significant physical examination findings (abnormalities) observed during the study will be reported as AEs. Any physical examination findings (abnormalities) persisting at the end of the study will be followed by the investigator until resolution or until reaching a clinically stable endpoint.

- **Electrocardiography**

Electrocardiograms (ECGs) will be recorded at Screening Visit and EOS/EW (Visit 3).

Twelve-lead ECGs will be recorded at a paper speed of 25 mm/sec so that the different ECG intervals (RR interval, PR interval, QRS interval, QT and QTc) can be measured automatically as per study site usual practice.

The ECG will be recorded with the subject in supine position after five minutes of rest until four regular consecutive complexes are available. ECG interval estimates will be measured as per study site usual practice, in this study.

Any clinically significant abnormalities will be recorded as AEs.

- **Clinical Laboratory Tests**

Blood samples will be collected at all study visits (Screening Visit [Visit 1], Day 2 [Visit 2], and End of Study/Early Withdrawal [Visit 3]) for the evaluation of haematology and serum chemistry.

Fresh urine samples will be collected at all study visits for dipstick urinalysis.

The investigator will review the safety laboratory test results, document the review, and record any clinically relevant result occurring or observed during the study in the AE section of the eCRF.

Haematology – the following parameters will be assessed: red blood cell (RBC) count, haemoglobin, haematocrit, mean corpuscular volume (MCV), mean corpuscular haemoglobin (MCH), mean corpuscular haemoglobin concentration (MCHC), white blood cell (WBC) absolute count (neutrophils, lymphocytes, monocytes, eosinophils, basophils, and others) and platelet count.

Blood Biochemistry – the following parameters will be assessed: urea, creatinine, creatinine clearance, total bilirubin, conjugated bilirubin, chloride, bicarbonate, sodium, potassium, calcium, phosphate, alkaline phosphatase (AP), aspartate aminotransferase (AST), alanine

aminotransferase (ALT), gamma-glutamyl transferase (GGT), albumin, total protein, total cholesterol, triglycerides, fasting glucose

Urinalysis – the following parameters will be assessed: pH, protein, ketones, bilirubin, blood, urobilinogen, nitrites, leukocyte esterase, glucose and specific gravity by dipstick.

Microscopy will be performed, if indicated, but results will not be collected in the eCRF. If in the opinion of the investigator there are any clinically significant abnormalities in microscopy, they will be recorded as an AE in the eCRF.

Pregnancy - A pregnancy test will be performed for all female subjects of childbearing potential at each visit: β -HCG test at Screening and End of study and urinary hCG test at Visit 2 Day 1 before IIP administration).

1.3.2.3 *Other assessments*

The following assessments will be performed at Screening visit (Visit 1), that will take place within the 2-week period prior to the first ^{68}Ga -OPS202 administration:

- Demographic data (year of birth/age, sex and race/ethnicity will be collected according to individual country regulations/requirements).
- Subject disposition information
- Medical and surgical history, including ongoing conditions
- Prior and concomitant medications/therapies
- Prior and concomitant non-drug therapies
- Concomitant surgical procedures
- Collection of historical paraffin embedded breast tumour blocks or slides with anatomical location of the lesion (s) indicated.

1.3.2.4 *Withdrawal/discontinuation*

A subject may discontinue participation in the study at any time for any reason (e.g. withdrawal of consent, AE). The investigator and/or sponsor can withdraw a subject from the study at any time for any reason (e.g. protocol deviation as defined in Section 13.1.2 of the protocol, noncompliance with the protocol conditions or AE). All cases of discontinuation will be discussed between the investigator and the sponsor.

The subject's participation in the study will be considered to have ended at the time of the last visit (Visit 3, at Day 14 \pm 3 days). For subjects who complete the study, final evaluations will be performed on Day 14 (\pm 3 days) after the subject receives the IIP.

If a subject decides to withdraw from the study after the administration of IIP, or the investigator decide to withdraw the subject, all efforts will be made to complete and report the observations up to the time of withdrawal as thoroughly as possible. A complete final evaluation at the time of the subject's withdrawal should be made and an explanation given of why the subject is withdrawing or being withdrawn from the study.

In case subject is lost to follow-up, date of termination will be specified, and the EW visit will be performed if possible.

1.3.3 Schedule of assessments

The schedule of procedures and assessments during the study is summarised in Table 1.

Table 1 Study Procedures and Assessments

Study Visits [a]	Screening Visit 1 Day -14 to -1	Visit 2[a] Day 1	Visit 2[a] Day 2	End of Study/Early Withdrawal Visit 3 Day 14 (±3)
Informed consent [b]	X			
Eligibility criteria	X	X		
Demographics [c]	X			
Medical history [d]	X			
Prior therapies [d]	X			
Concomitant therapies [e]	X	X	X	X
Physical examination [f]	X	X		X
Vital signs [g]	X	X	X	X
ECG [h]	X			X
Haematology [i]	X		X	X
Blood chemistry [j]	X		X	X
Urinalysis [k]	X		X	X
Pregnancy test [l]	βHCG (blood test)	Urinary HCG		βHCG (blood test)
⁶⁸ Ga-OPS202 PET/CT imaging [m]		X		
¹⁸ F-FDG-PET scan [n]	Any time during the study period			
Contrast enhanced CT [m]	With ⁶⁸ Ga-OPS202 PET or ¹⁸ F-FDG-PET			
Adverse events [o]	X	X	X	X
Compliance [p]		X		
Biopsy [q]	X			

AE=adverse event, CT=computed tomography, ECG=electrocardiogram, ¹⁸F-FDG=¹⁸F-fluorodeoxyglucose, HCG=human chorionic gonadotropin, HER2= human epidermal growth factor receptor 2, ICL=imaging core laboratory, IIP=investigational imaging product, PET=positron emission tomography.

- (a) **Study visits:** Screening Visit up to 14 days before IIP administration; Subjects may be hospitalised overnight at the discretion of the investigator at Visit 2. All subjects (either hospitalised or not) will attend consultation on Day 2, which is part of Visit 2, for: review of AEs, new or changed concomitant medications, vital signs, physical examination, haematology, biochemistry, urinalysis.
- (b) **Informed consent:** Must be obtained prior to undergoing any study specific procedures and will occur prior to the 2-week screening period.
- (c) **Demographics:** Age, sex and self-reported race/ethnicity if authorised to be collected in the country.
- (d) **Medical history and prior therapies:** To include clinically significant diseases, surgeries, cancer history and all relevant medications.
- (e) **Concomitant medications:** Dose and indication will be recorded from 3 months prior to the IIP administration, at study entry and at each visit. Once the subject has withdrawn from/completed the study, concomitant medications and treatments should be recorded until all study treatment-related toxicities have resolved.
- (f) **Physical examination:** Major body systems, body weight, height (screening visit only)

- (g) **Vital signs:** 0.5, 1, 2 and 4 hours post-injection (supine and standing systolic and diastolic blood pressure and heart rate, body temperature, respiratory rate).
- (h) **ECG:** Twelve-lead ECGs will be recorded at a paper speed of 25 mm/sec so that the different ECG intervals (RR, PR, QRS, QT) can be measured automatically as per study site usual practice. The ECG will be recorded with the subject in supine position after five minutes of rest until four regular consecutive complexes are available.
- (i) **Haematology:** Red blood cell (RBC) count, haemoglobin, haematocrit, mean corpuscular volume (MCV), mean corpuscular haemoglobin (MCH), mean corpuscular haemoglobin concentration (MCHC), white blood cell (WBC) count with differential (neutrophils, lymphocytes, monocytes, eosinophils, basophils, and others) and platelet count.
- (j) **Blood chemistry:** urea, creatinine, creatinine clearance, chloride, bicarbonate, sodium, potassium, calcium, phosphate, total bilirubin, conjugated bilirubin, alkaline phosphatase, aspartate aminotransferase, alanine aminotransferase, gamma-glutamyl transferase, albumin, total protein, total cholesterol, triglycerides, fasting glucose.
- (k) **Urinalysis:** Dipstick for pH, protein, ketones, bilirubin, blood, urobilinogen, nitrites, leukocyte esterase, glucose and specific gravity.
- (l) **Pregnancy test:** A pregnancy test will be performed at each visit particularly before ⁶⁸Ga-OPS202 administration.
- (m) **⁶⁸Ga-OPS202 PET/CT imaging:** PET acquisition at 0.5, 1 and 2 hours after ⁶⁸Ga-OPS202 administration. Iodinated i.v. CT contrast imaging (chest, abdomen, pelvis and brain). A single contrast enhanced computed tomography (ceCT) scan is required for the study. This can be acquired after either of the two PET scans (¹⁸F-FDG-PET or ⁶⁸Ga-OPS202 post the 2-hour acquisition). Low-dose CT scans will be acquired for the other PET scans where the ceCT is not obtained (see the Imaging Review Charter (IRC)). Anonymised and blinded to acquisition time images will be sent to the ICL.
- (n) **¹⁸F-FDG-PET scan:** ¹⁸F-FDG-PET scan, which is part of routine clinical diagnosis, will be performed during the study period and images sent to ICL. A ceCT or a low dose CT may be performed with the ¹⁸F-FDG-PET (see the Imaging Review Charter (IRC))
- (o) **Adverse events:** Subjects must be followed for AEs, regardless of relationship to IIP, from the time they signed the informed consent until 14±3 days after the dose of IIP. Clinically significant changes in physical examination, vital signs, electrocardiogram and laboratory findings will be recorded as an AE. The investigator will follow-up AEs until resolution or stabilisation.
- (p) **Compliance:** The peptide mass dose and the radioactivity dose injected will be recorded at Visit 2.
- (q) **Biopsy:** To be performed if not already done. Tumour biopsy, which is not a prerequisite for inclusion, is routinely performed for confirmation and staging of the disease, as well as classification according to hormone receptor status and HER2 status. For the study, an archived tumour sample (block is preferred over paraffin embedded slides) is required for the evaluation of sstr2 expression by immunohistochemistry staining.

1.3.4 Planned sample size

It is anticipated that a total of 54 subjects will be enrolled in the study for ⁶⁸Ga-OPS202 screening, to obtain around 16 sstr2 positive BC evaluable subjects. Considering the estimated prevalence of sstr2 overexpression in breast cancer, the overall number of subjects to be administered ⁶⁸Ga-OPS202 in the study will be over 50. However, when the ICL identifies 16 sstr2 positive evaluable subjects, with a minimum of two subjects with advanced disease, the study will be complete.

This estimation of 16 sstr2 positive BC evaluable subjects is considered appropriate for a descriptive analysis and it is not based on a formal statistical sample size calculation. In the event that a subject misses an imaging exam and/or measurement relevant to the primary and key secondary endpoints, an additional subject will be recruited to ensure an adequate sample size in the sstr2 positive BC evaluable set.

2 SUBJECT POPULATIONS (ANALYSIS SETS)

[figure not shown]
The following populations will be used during statistical analyses:

- **Eligibility screened population:** All subjects screened (i.e. who signed the informed consent).
- **Safety population:** All subjects who received the dose of study IIP.

- **^{68}Ga -OPS202 screened population:** All subjects who received the dose of study IIP and for whom PET/CT scan images are readable for at least one timepoint. This population encompasses both subjects with sstr2 positive lesion(s) and those with sstr2 negative lesions (no avid lesion with ^{68}Ga -OPS202).
- **Sstr2 positive population:** All subjects who received the dose of study IIP and for whom ^{68}Ga -OPS202 PET/CT scan images are readable for at least one timepoint and have one avid lesion identified by central readers, ^{18}F -FDG-PET/CT scan and a ceCT scan confirmed by the central readers.
- **Sstr2 positive evaluable population:** ^{68}Ga -OPS202 sstr2 positive population with at least two evaluable ^{68}Ga -OPS202 timepoints, ^{18}F -FDG-PET/CT scan and a ceCT scan confirmed by the central readers. A ^{68}Ga -OPS202 timepoint is considered evaluable if it shows at least one avid lesion.

Study populations are summarized in the figure below.

Figure 4 Study populations

For each population of analysis, further description and specificities are provided below.

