- (6) The ^{68}Ga -OPS202 PET scans will be compared with the ^{18}F -FDG-PET scan (with ceCT).

(a) Primary Efficacy Endpoint and Evaluation

The co-primary endpoint is therefore calculated in the following way:

- (1) The number of subjects with newly diagnosed breast cancer with primary sstr2 positive lesions identified by ^{68}Ga -OPS202 at any timepoint, divided by the total number of subjects imaged to obtain the prevalence in this study population.
- (2) The identification of the optimum acquisition time(s) based on differences in the number of lesions identified at each scan, and the reader interpretation of the optimum image in the primary breast lesions. The optimum image acquisition time could be one, two or all three acquisitions timepoints i.e. no noticeable difference between 0.5, 1 and 2 hours post infusion.

(b) Secondary Efficacy Endpoints and Evaluations*Key Secondary Endpoint:*

- Differences in the number of lesions detected by ^{68}Ga -OPS202 between the three PET acquisition timepoints (0.5, 1 and 2 hours), and reader interpretation of optimal image(s) in nodular and metastatic lesions. Significant uptake of ^{68}Ga -OPS202 for the evaluation of a lesion is an avid lesion defined by the blinded readers at one of the acquisition timepoints as an easily identifiable lesion radiologically, where there has been clear focal uptake of ^{68}Ga -OPS202 and 1.5-fold or greater uptake than in the non-tumoural liver and lung parenchyma.
- The SUV_{mean} and SUV_{max} in the primary lesion between each of the three timepoints, measured in the most avid lesions (using the ^{68}Ga -OPS202 scans). This is assessed by the tumour-to-background ratio in the primary tumour and each of the major anatomic sites (liver, lymph nodes, bone, lungs and brain); the background consists of non-tumoural liver parenchyma or aortic blood where sufficient liver is not available. Identification of lesions to be used will be made by one of the two primary readers.

Other Secondary Endpoints:

- Comparison to standard-of-truth for the primary breast tumour:
 - $(^{68}\text{Ga}\text{-OPS202 PET/CT}) / (^{18}\text{F}\text{-FDG-PET/CT})$
 - For each acquisition time of ^{68}Ga -OPS202 PET.

This will be repeated for each of the other anatomical locations:

- Lymph nodes
- Liver
- Axial/appendicular skeleton
- Lungs
- Brain

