7.1 Eligible and Evaluable Subjects

- All subjects who receive ^{68}Ga -OPS202 are “eligible” subjects and will be included in the safety analysis.
- All eligible subjects with one or more readable ^{68}Ga -OPS202 PET and a readable ceCT scan will be included in the first component of the co-primary endpoint analysis to determine sstr2 positive prevalence.
- The following describes those subjects that are eligible and “evaluable” for the second component of the co-primary endpoint to assess the optimum timing of the PET scan following infusion of ^{68}Ga OPS202:
 - A readable ceCT scan
 - At least two ^{68}Ga -OPS202 PET scans that are readable (three images are to be acquired but 2 of these, MUST be readable by the central readers; if only two PET scans are acquired BOTH must be readable) with at least one avid lesion identified by central readers.

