2.1 Efficacy populations

2.1.1 *⁶⁸Ga-OPS202 screened population*

The ⁶⁸Ga-OPS202 screened population includes all subjects who received the dose of study IIP with one or more readable ⁶⁸Ga-OPS202 PET and a readable ceCT scan.

The assessment of ⁶⁸Ga-OPS202 PET scan and ceCT scan readability will be based on the imaging read named “Confirmation read”, provided by ICL.

This population encompasses both subjects with sstr2 positive lesion(s) and those with sstr2 negative lesions (i.e. no avid lesion with ⁶⁸Ga-OPS202).

2.1.2 *Sstr2 positive population*

The sstr2 positive population includes all subjects who received the dose of study IIP and for whom ⁶⁸Ga-OPS202 PET/CT scan images are readable for at least one timepoint and have one avid lesion identified by central readers.

The assessment of ⁶⁸Ga-OPS202 PET scan readability and the presence of avid lesions will be based on the imaging read named “Confirmation read”, provided by ICL.

Subjects are also required to have a ¹⁸F-FDG-PET/CT scan and a readable ceCT scan.

2.1.3 *Sstr2 positive evaluable population*

The sstr2 positive evaluable population includes all subjects from the ⁶⁸Ga-OPS202 sstr2 positive population with at least two evaluable timepoints. Subject are also required to have a ¹⁸F-FDG-PET/CT scan and a readable ceCT scan.

Evaluable subjects are those with a ceCT scan, ¹⁸F-FDG-PET scan and at least two ⁶⁸Ga-OPS202 PET scans that are readable (three images are to be acquired but two of these must be readable by the central readers. If only two PET scans are acquired both must be readable) with at least one avid lesion identified on at least 2 timepoints by central readers.

The assessment of ⁶⁸Ga-OPS202 PET scan readability and the presence of avid lesions will be based on the blinded imaging read “⁶⁸Ga-OPS202 PET Independent Review” (two readers and potential adjudication), provided by ICL.

Listings of subjects regarding inclusion in each population and satisfying the population definition and associated data will be reviewed by the study team.

The reasons for subject exclusion from each of the populations will be listed and tabulated.

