3.2.1.1 Primary efficacy analysis

First component of the co-primary endpoint

The first component of the co-primary endpoint is the percentage of subjects with sufficiently avid lesion(s) to be identified as a sstr2 positive lesion, i.e. the sstr2 positive prevalence in this study population. Avid is defined by the blinded readers at one of the timepoints as an easily identifiable lesion radiologically, where there has been clear focal uptake of ⁶⁸Ga-OPS202.

This will be a simple percentage calculation:

$$\begin{aligned} & \text{Percentage of subjects with avid lesion identified as sstr2 positive lesion} \\ &= \frac{\text{Number of subjects in sstr2 positive population}}{\text{Number of subjects in } ^{68}\text{Ga} - \text{OPS202 screened population}} \end{aligned}$$

A listing with the subjects in sstr2 positive population and the subjects in the ⁶⁸Ga-OPS202 screened population will be provided in order to allow computing this percentage.

Second component of the co-primary endpoint

The second component of the co-primary endpoint is based on both image quality and lesion count using the sstr2 positive evaluable population.

The selection of the optimal PET acquisition time will be done by choosing the timepoint with superior images based on overall image quality and observed higher number of lesions detected.

The number of lesions detected by ⁶⁸Ga-OPS202 in the primary breast lesions will be reported at each of the three PET acquisition timepoints (0.5, 1 and 2 hours).

Individual values of number of lesions detected by ⁶⁸Ga-OPS202 in the primary breast lesions (result from both readers as well as final result) will be listed by subject and by PET acquisition timepoint.

Image quality

After blinded reading, the readers will compare the three scans (the three acquisitions of ⁶⁸Ga-OPS202) contemporaneously for each subject and note which image(s), if any, provides superior images based on overall image quality and lesion count.

This qualitative assessment will be performed using a quality score.

For each PET/CT assessment, each independent blinded reader will perform a direct comparison of the three ⁶⁸Ga-OPS202 scans acquired at different times (0.5, 1 and 2 hours) in the primary breast lesions. The readers will be allowed to select whether one, two or all three acquisitions are optimal, attributing a score for each assessment. The readers will be blinded to timepoint sequence.

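### The denominator of the first co-primary percentage is defined inconsistently with respect to the contrast-enhanced CT, and the numerator carries scan conditions that the denominator may lack

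*SAP*

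**What the plan says.** SAP 3.2.1.1 defines the first co-primary component as a simple ratio. The numerator is "Number of subjects in sstr2 positive population" and the denominator is the size of the 68Ga-OPS202 screened population. Protocol 11.4.4 gives the same ratio, and SAP 2.3 and Protocol 11.1.1 name the same denominator.

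The denominator is worded in three ways:

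- **SAP 2 and Protocol 11.1:** women who were dosed "and for whom PET/CT scan images are readable for at least one timepoint". There is no ceCT condition.
- **SAP 2.1.1 and Protocol 7.1:** a readable ceCT is needed as well. SAP 2.1.1 asks for one or more readable OPS202 "PET and a readable ceCT scan". Protocol 7.1 ties this to the endpoint itself: subjects with one or more readable OPS202 "PET and a readable ceCT scan will be included in the first component of the co-primary endpoint analysis to determine sstr2 positive prevalence".
- **Protocol 7(a):** the count of positive women is "divided by the total number of subjects imaged to obtain the prevalence in this study population".

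The numerator population is stricter throughout. SAP 2 and Protocol 11.1 require an avid lesion plus an FDG "PET/CT scan and a ceCT scan confirmed by the central readers". SAP 2.1.2 requires an FDG "PET/CT scan and a readable ceCT scan".

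**The concern.** A proportion is coherent when its numerator consists of those members of the denominator who have the feature. Here the numerator carries scan conditions that the denominator may not. Under the SAP 2 / Protocol 11.1 wording, a woman with a clearly avid lesion but no readable ceCT stays below the line and cannot appear above it, so she is reported as if she were sstr2 negative. Under SAP 2.1.1 / Protocol 7.1 she is in neither count. Two programmers following different sections could therefore report different percentages from the same data.

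This matters more than a routine wording slip. The endpoint is co-primary. After the decision to terminate early, SAP 5 says that efficacy endpoints are not tabulated, and SAP 3.2.1.1 supplies a listing of the two populations from which the percentage is computed. The population definitions are in effect the whole analysis. With limited data, each woman also carries more weight.

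**Working it through.** **1. Can a readable PET/CT exist without a ceCT?** Yes. SAP 1.2 and Protocol 3.1 require one ceCT, which may be taken with either the FDG or the OPS202 PET; low-dose CT accompanies the other scans. A readable OPS202 PET/CT timepoint therefore does not establish that a readable ceCT exists.

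**2. The plan's own figure.** SAP 1.3.4 plans 54 women imaged to obtain around 16 sstr2 positive evaluable women, and 16/54 = 29.6%. No expected prevalence is stated. An assumed 30% gives 16/0.30 = 53.3, rounded up to 54, which is consistent but remains an assumption.

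**3. Notation.** Let N = 54 be the women with at least one readable OPS202 timepoint, and P = 16 the positives who have the required scans. Let m be the women without a readable ceCT, and a those among the m who have an avid lesion. Neither m nor a is in the documents, so both are assumed.

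- Wording A (SAP 2, Protocol 11.1): P/N
- Wording B (SAP 2.1.1, Protocol 7.1): P/(N − m)
- No ceCT condition on either side: (P + a)/N
- Gap between B and A: P·m / [N(N − m)]

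| m | a | A | B | No ceCT condition |
|---|---|---|---|---|
| 0 | 0 | 16/54 = 29.6% | 16/54 = 29.6% | 16/54 = 29.6% |
| 3 | 0 | 16/54 = 29.6% | 16/51 = 31.4% | 16/54 = 29.6% |
| 3 | 3 | 16/54 = 29.6% | 16/51 = 31.4% | 19/54 = 35.2% |
| 5 | 0 | 16/54 = 29.6% | 16/49 = 32.7% | 16/54 = 29.6% |

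For m = 3 the gap is 16 × 3 / (54 × 51) = 1.7 points. For m = 5 it is 16 × 5 / (54 × 49) = 3.0 points. When the 3 women are avid, wording A understates the figure without a ceCT condition by 3/54 = 5.6 points.

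**4. A smaller study (all figures assumed).** Take 20 imaged, 5 positives with a ceCT, and 2 women without one, of whom 1 is avid. A gives 5/20 = 25.0%, B gives 5/18 = 27.8%, and no ceCT condition gives 6/20 = 30.0%.

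**5. Protocol 7(a).** If all 54 imaged women have a readable timepoint, this denominator equals that of wording A. Any imaged woman with no readable timepoint enlarges it further. Its numerator refers to primary lesions and names no ceCT, so it matches neither A nor B.

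**6. The FDG condition.** Neither A nor B requires an FDG scan. Suppose one further woman among the 54 is avid and has a readable ceCT but no FDG-PET/CT. The reported figure under A stays at 16/54 = 29.6% instead of 17/54 = 31.5%. Under B with m = 3 it stays at 16/51 = 31.4% instead of 17/51 = 33.3%. Aligning the ceCT condition alone therefore does not make the proportion coherent.

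**The case against.** The strongest reply is that the SAP has an operative definition. Section 2 gives short entries and announces fuller detail below. Section 2.1.1 then adds the ceCT and names the core laboratory's Confirmation read as the source for judging its readability. Protocol 7.1, which addresses this endpoint directly, agrees. That makes a programming error less likely, but it does not settle the matter. Nothing says that 2.1.1 prevails over section 2, the protocol has the same split between 7.1 and 11.1, and SAP 5 records no change to this population. The populations figure in SAP 2 is not visible to this review and may bear on the point.

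It can also be said that the event may be rare. The ceCT is mandatory, women who cannot tolerate contrast are excluded, and Protocol 3.1 arranges a missing ceCT at Day 2. This stands: the effect may be small or zero. At the planned size, a shift of 1.7 points is small beside a Wilson 95% interval of about 19% to 43% for 16/54. The analysis is descriptive and involves no test.

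Finally, reasons for exclusion from each population are to be listed and tabulated. That helps only in part, because an unreadable ceCT is a reason for exclusion from the screened population under one wording and not under the other.

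A reader might infer that some of the planned 16 positives could lack a ceCT, so that three such women would give 13/54 = 24.1% or 13/51 = 25.5%. The documents do not support this. The planned 16 are evaluable positives, who have a ceCT by definition; avid women without one would be additional to them.

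**Conclusion.** The inconsistency is in the current text of both documents and should be resolved. Its size depends on a number that the documents do not give. It is zero if every imaged woman has a readable ceCT. With 54 imaged, 16 positives who have the required scans and 3 women without a readable ceCT, the reported percentage is 29.6% or 31.4%; if those 3 are avid, it is 35.2% with no ceCT condition.

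Two stronger readings are tempting and should be resisted. The first is that the reported prevalence is known to be wrong: nothing in the documents shows that any woman lacked a readable ceCT. The second is that only the wording without ceCT is at fault and that SAP 2.1.1 is sound as it stands: the FDG requirement in the numerator counts an avid woman without that scan as negative under either wording.

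**What to change.** 1. Use the SAP 2.1.1 / Protocol 7.1 definition of the screened population (dosed, at least one readable OPS202 PET, readable ceCT) in SAP 2, Protocol 11.1 and Protocol 7(a). If the protocol will not be amended, state in SAP 5 which definition applies.
2. For this endpoint, define the numerator as the members of that same set with at least one avid lesion. Attach no scan condition that the denominator lacks, including the FDG-PET/CT.
3. Report how many imaged women lack a readable ceCT.
4. Show the percentage once more with the ceCT condition removed from both numerator and denominator.

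The cost is a wording change and one or two extra lines in the output. The Confirmation read already supplies ceCT readability and the presence of avid lesions, so no new data should be needed, provided that it recorded avidity for women without a ceCT. The small downside is that women without a readable ceCT leave the main figure; step 4 shows what difference that makes.
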